3.6 Methods for ensuring blinding

Not applicable as this is an open-label study.

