- j For women of childbearing potential, defined as those who are not surgically sterile (i.e., bilateral tubal ligation, bilateral oophorectomy, or complete hysterectomy) or postmenopausal (defined as 12 months with no menses without an alternative medical cause): A blood sample to determine serum β hCG is required at screening; this sample will be analysed at the central laboratory for the study. Additionally, urine samples for a urine-based pregnancy test will be collected before dosing on Day -7 of the lead-in, before dosing on Day 1 of each cycle, and at the EOT visit. Urine-based pregnancy tests will be performed at the study centres.
- k Tumor assessments to be performed at screening, on Day 15 of Cycle 2 (i.e., at the beginning of Week 7), at the beginning of each subsequent even-numbered cycle, and at the EOT visit. Patients who are on study treatment for more than 24 months may have the frequency of tumor assessment reduced to every 12 to 16 weeks at the discretion of the Investigator. Patients who discontinue treatment for reasons other than PD will continue to undergo tumor assessments every 2 months (\pm 7 days) until PD is noted. To facilitate scheduling of tumor assessments, a window of \pm 7 days is allowed. For the additional 48 patients to be enrolled in first-line in Arms B7 and B8, a central imaging read will be done in addition to the local site RECIST evaluation. See Section 5.3.1 for additional details.

- ^l The reporting period for AEs and concomitant medication starts immediately following the time that written informed consent is obtained and ends 28 (+7) days after the last dose of study drug or until the initiation of subsequent anticancer therapy. For patients dose-reduced to levels -1 or -2 of AZD9150 in Arms B1, B3, or B7 who are experiencing treatment-related AEs of Grade 2 or lower, visits on Day 8 and Day 22 of each cycle (no AZD9150 dosing) may be considered optional, unless, in the Investigator's estimation, more frequent individual evaluations are appropriate.

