^a The results are averaged over the corresponding set of naïve and pretreated values. The expected sample size includes 12 patients in each of the 2 monotherapy arms.

Thus, with the study design and interim assessments as described above, the chance to stop a combination arm in anti-PD-(L)1 naïve patients given an optimistic true ORR value (0.45 for naïve and 0.31 for pretreated patients) is approximately 19.3%. The chance to stop a combination arm in anti-PD-(L)1 pretreated patients is approximately 11.7%. If the true ORR performance of the combination arms is low (i.e., approximately 10% for naïve, 5% for pretreated), the chance that any combination will stop before fully recruiting is >98% for naïve and >94% for pretreated.

Figure 9 Adaptive approach to sample size Part B (B1-B6)

If at least 2 CR or PR are observed in the first 20 patients in either of the 2 pretreated expansion arms (Arm B1 or B2), then an additional 25-32 patients may be enrolled.

In addition, Arms B7 and B8 will enroll patients who have not received prior systemic treatment for RM SCCHN and will receive combination treatment of AZD9150 in combination with MEDI4736. With approximately 48 patients in each arm, the chance that fewer than 12 patients with CR or PR (responding) will be observed, given the true fraction of patients responding is 35%, is 9%. The chance that at least 15 patients responding is observed, given the true fraction of patients responding is 25%, is 20%. In addition, B8 will incorporate predictive power monitoring for futility beginning with the 15th patient. If at any time from the 15th patient through the 48th patient, the chance to observe 13 responses in 48 patients falls below 20%, then the arm will be stopped.

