## Statistical Analysis Plan

maximum of 35 efficacy evaluable patients following the interim analysis if at least 5 of 20 patients have responded with at least a PR.

For each combination arm in the anti-PD-(L)1 pretreated patients (Arms B1 and B2); a predictive probability will be calculated to assess the chance of observing at least 3 of 20 responses (either PR or CR) following 10 efficacy evaluable patients in each arm. If the predictive probability falls below 20% within an arm, then the corresponding arm will be stopped. However, no formal interim analysis will be conducted for the combination arms in the anti-PD-(L)1 pretreated patients.

Recruitment will continue while predictive power is measured. If an arm is to be stopped, no new patients will be recruited but patients who are already on study will continue in accordance with study guidelines outlined in Section 4 of the protocol Amendment 9.

If at least 2 CRs or PRs are observed in the first 20 patients in either of the 2 pretreated expansion arms, an additional 25 to 32 patients may be enrolled to that particular pretreated combination arm.

Predictive power monitoring will not be performed for the 2 monotherapy groups (B5 and B6) in dose-expansion Part B. The 2 monotherapy arms will continue recruiting until 12 efficacy evaluable patients have been enrolled in each arm.

In addition, Arms B7 and B8 will enroll patients who have not received prior systemic treatment for recurrent and/or metastatic squamous cell cancer of the head and neck (RM-SCCHN) and will receive combination treatment of AZD9150 in combination with MEDI4736. With approximately 48 patients in each arm, the probability of observing  $\leq 12$  responses (CR or PR) out of 48 patients is 9%; given the true probability of responses is 35%. The probability of observing  $\geq 15$  responses (CR or PR) out of 48 patients is 20%, given the true probability of responses is 25%. In addition, B8 will incorporate predictive power monitoring for futility beginning with the 15th patient. If at any time from the 15th patient through to the 48th patient, the chance to observe 13 responses in 48 patients falls below 20%, then the arm will be stopped.

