In the anti-PD-(L)1 pretreated patients (B1 and B2), approximately 10 to 52 patients will be treated in each of the 2 combination therapy arms. Once efficacy outcomes have been observed in the first 10 efficacy evaluable patients in each arm, a predictive power calculation will be used to assess the chance of observing at least 3 of the 20 responses (either partial or complete) in each arm. Predictive power (chance to observe at least 3 of 20 responses) will be recalculated following the observation of the efficacy outcome in each efficacy evaluable patient as they were dosed in the trial. If, following the observation of any patient's outcome, predictive power falls below 20%, the arm in which this happens will be stopped. However, no formal interim analysis will be conducted for the combination arms in the anti-PD-(L)1 pretreated patients.

In addition, Arms B7 and B8 will enroll patients who have not received prior systemic treatment for RM SCCHN and will receive combination treatment of AZD9150 in combination with MEDI4736. With approximately 48 patients in each arm, the probability of observing  $\leq 12$  responses (CR or PR) out of 48 patients is 9%, given the true probability

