## Statistical Analysis Plan

response will be used, not the confirmatory scan date. If there are more than one RECIST assessment which contributes to a particular visit, e.g. two different body areas, the later of the two would be used to declare CR/PR.

Best overall response (BOR) will be determined programmatically based on RECIST using all site investigator data up until the first progression event. The denominator will be consistent with that used in the ORR analysis.

For patients whose progression event is death, BOR will be calculated based upon all evaluable RECIST assessments prior to death.

For patients who die with no evaluable RECIST assessments, if the death occurs  $\leq 18$  weeks (i.e., 16 weeks + 2 week to allow for a late assessment within the assessment window) after first dose/administration of study medication, then BOR will be assigned to the progression (PD) category. For patients who die with no evaluable RECIST assessments, if the death occurs  $> 18$  weeks after start of treatment then the patient will be counted as a non-responder and BOR will be assigned to the NE category.

A patient will be classified as a responder if the RECIST criteria for a confirmed CR or PR are satisfied at any time following first dose/administration of study medication, prior to RECIST progression and prior to starting any subsequent cancer therapy.

The number and percentage of patients in each of the overall response categories will be reported by treatment group using the Efficacy Set. The best overall response will be listed for each patient.

For Part A, only descriptive summaries of the best overall response will be provided. For Part B, exact 2-sided 80% CIs will be computed for each response level using the method of Clopper-Pearson (Clopper and Pearson 1934).

The Independent Central Review (ICR) adjudicated results of imaging data will be obtained from Paraxel. The data will be used in the standardization of radiological exams from the Investigator Sites for this trial. The objective will be to assess the concordance rate of BOR at both the sample and patient level for the following:

- Best Independent Central Review (BICR) response results compared to programmatically derived BOR
- BICR response results compared to the investigator assessment of BOR, and
- Investigator assessment of BOR compared to programmatically derived BOR.

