## Statistical Analysis Plan

A contingency table containing the relevant data on the absolute and percentage of agreement and disagreement will be provided, alongside the Cohen's kappa to indicate the level of agreement among pairs of (ICR, investigator and programmatically derived) BOR determinations. In addition, three separate agreement plots among pairs of (ICR, investigator and programmatically derived) BOR determinations and individual patient listings of (ICR, investigator and programmatically derived) BOR determinations will be provided.

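### The planned central read of arms B7 and B8 yields BOR agreement outputs but no central-read confirmed ORR with an 80% CI beside the site-based primary result

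*SAP*

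**What the plan says.** Protocol 3.5 makes B7 and B8 non-randomised arms. On blinding, Protocol 3.6 says "Not applicable as this is an open-label study".

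SAP 8.2.2 makes ORR the primary efficacy endpoint of Part B, reported by treatment group with an exact two-sided 80% Clopper-Pearson interval. A response must be confirmed at least 4 weeks later, and a response first seen after another anticancer therapy does not count. SAP 8.3.2 states that BOR is derived programmatically from the site investigators' data.

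For B7 and B8, Protocol Table 5 (note k) adds that "a central imaging read will be done in addition to the local site RECIST evaluation". SAP 8.3.2 says the adjudicated central results will be obtained and will serve to standardise the sites' radiology. It then sets the purpose: "The objective will be to assess the concordance rate of BOR at both the sample and patient level for the following" pairings, namely central against derived BOR, central against investigator BOR, and investigator against derived BOR. The outputs are a contingency table of agreement and disagreement, Cohen's kappa "to indicate the level of agreement among pairs of (ICR, investigator and programmatically derived) BOR determinations", three agreement plots and patient listings of all three determinations.

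Neither SAP 8.2.2, 8.3.1 and 8.3.2 nor SAP 13 plans an ORR computed from the central read.

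**The concern.** With no concurrent control and no between-arm efficacy inference (SAP 8), the absolute ORR and its interval are the evidence from B7 and B8. Protocol 1.2 justifies the first-line arms by setting the trial's response rate against published monotherapy rates of 11%, 13.3% and 16%, and expects the results to inform decisions on later studies. Generous site reading would inflate exactly that kind of external comparison. Deriving BOR by program does not remove the risk, because lesion selection, measurement and calls on non-target or new lesions are still made at an unblinded site.

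A central read is the natural check on this, and one is planned. The question it should answer is what the ORR would be if the central reader were used. Kappa and percent agreement answer a different question: they treat a site response downgraded centrally and a site non-response upgraded centrally almost alike.

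**Working it through.** **Inputs.** "With approximately 48 patients in each arm" (SAP 3.6.2), so n = 48. The interval is the exact two-sided 80% Clopper-Pearson (SAP 8.2.2). The documents give no expected discordance between readers, so every discordance pattern below is an assumption.

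**The plan's own figures.** SAP 2.2 says of 12 or fewer "responses (CR or PR) out of 48 patients is 9%; given the true probability of responses is 35"%. The exact binomial gives P(X ≤ 12 | 48, 0.35) = 0.094, which agrees. Protocol 8.2.2 says "The chance that at least 15 patients responding is observed, given the true fraction of patients responding is 25%, is 20"%; P(X ≥ 15 | 48, 0.25) = 0.200, which agrees. Protocol 8.2.2 words the lower mark differently: "fewer than 12 patients with CR or PR (responding) will be observed, given the true fraction of patients responding is 35%, is 9"%. P(X < 12 | 48, 0.35) = 0.051, so the 9% fits only the SAP wording. That is a separate discrepancy, but it means 12/48 lies at or below the SAP's lower mark and not below the protocol's.

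**Illustration.** Sites score 15 responders, the central read upholds 12 of them, and it adds none.

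- Observed agreement: (12 + 33)/48 = 45/48 = 0.9375.
- Chance agreement: (15 × 12 + 33 × 36)/48² = (180 + 1188)/2304 = 0.594.
- Kappa: (0.9375 − 0.594)/(1 − 0.594) = 0.846.
- Site ORR: 15/48 = 31.3%, 80% CI 22.4% to 41.4%.
- Central ORR: 12/48 = 25.0%, 80% CI 16.9% to 34.8%.

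The estimate moves by 3/48 = 6.3 percentage points. The interval goes from including 35%, the optimistic rate used in sizing the arm, to excluding it.

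**Range of assumed one-way discordance, central read fixed at 12/48**

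| Site responders | Site ORR (80% CI) | Agreement | Responder kappa |
|---|---|---|---|
| 13 | 27.1% (18.7-37.0) | 97.9% | 0.95 |
| 15 | 31.3% (22.4-41.4) | 93.8% | 0.85 |
| 16 | 33.3% (24.3-43.5) | 91.7% | 0.80 |
| 18 | 37.5% (28.1-47.8) | 87.5% | 0.71 |

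**Kappa on the full BOR scale.** The SAP applies kappa to BOR, not to responder status. Assume the sites record 2 CR, 13 PR, 14 SD, 16 PD and 3 NE, and the central read moves three PR to SD. Unweighted kappa is then 0.91. The SAP does not say whether kappa is weighted.

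**Does kappa register direction?** Take four disagreements in 48. All four one way (16 against 12) give (0.917 − 0.583)/(1 − 0.583) = 0.800. Two each way, with both reads at 14 responders, give 0.798. In the first case the ORRs differ by 4/48 = 8.3 points; in the second they are equal.

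**Would a test of bias help?** Exact McNemar for three one-way disagreements gives p = 2 × 0.5³ = 0.25. At this sample size, two estimates side by side tell the reader more than a test.

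**The case against.** The strongest reply is that the information is already there. In a table of central against derived BOR, the margins give the central CR + PR count, the off-diagonal cells give the direction of each reclassification, and the listings identify the patients. SAP 8 also has a general rule that Part B efficacy data are summarised by treatment group with 80% intervals, and the table shells are in a separate document that is not available here. This stands in part: direction is recoverable. But a table margin does not replace a defined estimate. SAP 8.3.2 does not say that the central BOR follows the primary analysis on 4-week confirmation, the subsequent-therapy exclusion or the denominator, nor that the agreement outputs are by arm. The general rule attaches intervals to planned estimates, and a central-read ORR is not among them.

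A second reply is that the illustration is chosen. All three discordances run one way, the two intervals overlap widely, and p = 0.25 cannot separate them from chance. That is correct. The example shows what the agreement summaries can conceal; it is not evidence that site bias exists.

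A third is that programmatic derivation and the confirmation requirement limit site discretion. They do so when the response is assigned, but not when lesions are measured.

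A reader might go further and infer that the central read feeds kappa alone, that reading bias would be invisible, or that three patients would decide the arm's outcome. The documents do not support this. A contingency table, plots and listings are planned as well. No kappa threshold is set, so nothing formally passes. The marks at 12 and 15 of 48 describe operating characteristics and carry no decision. B7 has no predictive-power monitoring, and B8 has futility monitoring only, against 13 of 48.

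**Conclusion.** The gap is real but modest. For two open-label, non-randomised arms whose evidence is an absolute ORR, the plan obtains independent reads and does not turn them into a comparable ORR with an interval. The summary measures it does plan, percent agreement and kappa, are nearly blind to direction. Under the assumed one-way discordance of three patients in 48, agreement of 93.8% and responder kappa of 0.85 accompany a 6.3-point fall in ORR, and the 80% interval no longer reaches 35%. The size rests wholly on that assumption; one to six one-way disagreements would move the ORR by 2.1 to 12.5 points (1/48 to 6/48). The primary analysis itself need not change. The point is a worthwhile, low-cost improvement, not an error that invalidates the plan.

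**What to change.** Add to SAP 8.2.2 a sensitivity analysis of the primary endpoint, separately for B7 and B8:

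- confirmed ORR by central read with its exact 80% Clopper-Pearson interval, shown beside the site-based ORR;
- the same Efficacy Set denominator, 4-week confirmation rule and subsequent-therapy exclusion as the primary analysis;
- centrally unevaluable patients counted as non-responders;
- the site-by-central responder 2x2 table by arm, so that reclassifications in each direction can be seen.

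Keep kappa, the plots and the listings as supporting output. Write the rules before the central results are examined, including how central confirmation and central progression are dated; otherwise these choices become post hoc.

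The cost is a few lines of specification and a little extra programming. SAP 8.3.2 already provides for obtaining the central results, so no new data collection is needed. The drawback for the sponsor is that the central ORR may be lower than the site-based figure.

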## Statistical Analysis Plan

A contingency table containing the relevant data on the absolute and percentage of agreement and disagreement will be provided, alongside the Cohen's kappa to indicate the level of agreement among pairs of (ICR, investigator and programmatically derived) BOR determinations. In addition, three separate agreement plots among pairs of (ICR, investigator and programmatically derived) BOR determinations and individual patient listings of (ICR, investigator and programmatically derived) BOR determinations will be provided.

### 8.3.3. Duration of Overall Response (DOR)

The duration of response (DOR) is defined as the time from the date of first documented response (CR or PR) until the date of documented progression or death in the absence of disease progression. The time of the initial response will be defined as the latest of the dates contributing towards the first visit response of CR or PR. The end of response should coincide with the date of progression or death from any cause used for the progression-free survival (PFS) endpoint. If progression or death due to any cause does not occur after a response, the patient's DOR will be censored at the date of last tumour assessment (i.e., the PFS censoring time). Only patients who have a CR or PR during the study will be included in the analysis.

The DOR in weeks will be calculated for all patients that experience documented CR or PR during the study in weeks as follows:

$$\text{Duration of response (weeks)} = ((\text{Date of Progression/Death/Censoring} - \text{Date of First recorded CR or PR}) + 1)/7.$$

If there are sufficient data, DOR will be analyzed for all evaluable patients achieving response during the study using a Kaplan-Meier (K-M) survival analysis. Only patients who have a confirmed response will be included in this summary table. A K-M curve will present the distribution of DOR time by treatment group, along with the median DOR, provided it has been reached by the time of analysis. In Part B only, two-sided 80% CIs will be provided for the median DORs (Brookmeyer and Crowley 1982). Swimmer plots that clearly show the profile of each patient who responds will be produced.

In Part B, the Expected Duration of Response (EDOR) will be calculated for each treatment arm by multiplying the proportion of patients responding to treatment and the mean DOR amongst responding patients. Two-sided 80% CIs will also be provided for the EDORs (Ellis et al 2008).

## Statistical Analysis Plan

For Part B only, a sensitivity analysis of DOR will be performed where patients who do not progress before dying will be censored at the time of the administrative end of the trial (i.e., the latest of the last known tumour assessment, the last date of collection of clinical laboratory or vital sign data, or the last date of telephone contact with the subject) rather than at the time of death. The K-M plot will show the distribution of this modified DOR by treatment group, along with the median value of the modified DOR and its two-sided 80% CI (Brookmeyer and Crowley 1982).

A single listing will provide values of DOR, PFS, and OS for individual patients and indicate whether the corresponding survival time was censored.

### 8.3.4. Durable Response Rate

A patient is said to have a durable response if they have a confirmed overall tumour response of either CR or PR that lasts at least 3 months following the initial confirmation of the response. For the purposes of this calculation, 3 months will be defined as 13 weeks or 91 days. The durable response rate, the percentage of patients who have a durable response, will be calculated using the number of patients in the Efficacy Set. The durable response rate will be summarized by treatment group. In Part B only, an exact 2-sided 80% CI for the durable response rate will be computed using the Clopper-Pearson method (Clopper and Pearson 1934).

### 8.3.5. Disease Control Rate (DCR)

A patient is said to have achieved disease control if they have a tumour response of SD, PR, or CR according to RECIST version 1.1 criteria. Disease control will be assessed at 12 weeks after the start of study drug and is defined as the proportion of all patients in the Efficacy set that have an overall visit response of SD, PR, or CR at Week 12. Therefore, earlier overall visit responses of CR or PR that become PD at Week 12 or NE responses at Week 12 do not constitute disease control at 12 weeks. A time window of 1 week around the Week 12 visit will be applied, and it is recommended that any visits occurring 11 weeks or more after dosing are acceptable; however, if an earlier visit is defined as PD, the overall visit response at Week 12 would also be defined as PD. If the Week 12 overall response is missing or NE but the next evaluable response is SD or better, the patient will be defined as having an overall visit response of SD, PR, or CR at 12 weeks.

For individual patients, disease control at the Week 12 visit will be derived using the algorithm shown in Table 6.

